6.8 Efficacy

For binary efficacy endpoints estimated as binomial proportions, the frequency and percentage of patients achieving the outcome will be presented by treatment group at each assessed study week. The primary analysis of these endpoints will use a Cochran-Mantel-Haenszel (CMH) test stratified by the different levels of the randomization stratification factors of BMI at Screening (<25 kg/m², ≥25 kg/m²), Week -2 A1C (≤9%, >9%), and use of CSII at Screening (Yes, No). The treatment group comparisons will be performed at Week 24 only. At other assessed study weeks, only descriptive statistics will be used to summarize the data. Point estimates of treatment effect and 2-sided 95% confidence limits (CLs) of the treatment effect (ie, LX4211 minus placebo) will be calculated at Week 24. The 95% CLs will be based on normal approximation methods using a continuity correction factor. Missing observations at Week 24 will be imputed as non-responders (ie, NRI); only the observed data will be summarized at the earlier study weeks. Endpoints comprised of multiple outcomes will use descriptive methods to summarize each component by treatment group at each study week.

Primary analysis of the continuous efficacy endpoints will use MMRM statistics based on the restricted maximum likelihood method for estimation. The analysis model will include treatment, randomization strata of BMI at Screening (<25 kg/m², ≥25 kg/m²), randomization strata of Week -2 A1C (≤9%, >9%), randomization strata of use of CSII at Screening (Yes, No), time (study week), and a treatment-by-time interaction as fixed categorical effects, and Baseline dependent variable-by-time interaction as a covariate. For the endpoint of percent change from Baseline, the analysis model will not include the interaction covariate. An unstructured (co)variance structure will be used to model the within-patient errors. Other structures will be explored by use of Akaike's information criteria should the unstructured (co)variance structure not result in model convergence. The Kenward-Roger approximation will be used to estimate the denominator degrees of freedom. The adjusted mean change from Baseline by each study week for each treatment group will be estimated in the framework of this model, as well as the between-group differences (comparing LX4211 to placebo) and the 95% CLs for the adjusted mean. All post-Baseline observations collected at scheduled visits will be used in the MMRM, including data collected after the discontinuation of study drug. An analysis of covariance (ANCOVA) will be applied where only 1 post-Baseline scheduled visit occurs; ie, the MMRM analysis omitting the time-related effects.

Summarization of the inferential statistics will include the Least Squares means (LS means), standard error (SE) of the estimates, p-values, and 2-sided CLs. These statistics will be provided for the within treatment group changes from Baseline and for the comparison of LX4211 versus placebo for the change from Baseline scores.

Statistical Analysis Plan

Version: Final 1.0

Lexicon Pharmaceuticals Protocol No. LX 4211.1-312-T1DM

Date of Issue: 17 MAR 2017

Covance Study ID: 000000145143

The test for superiority of LX4211 versus placebo based on the primary efficacy endpoint will be performed at the 2-sided 0.05 α -level. If this null hypothesis is rejected, a sequential procedure will be used to maintain the overall Type I error rate at a 2-sided, 0.05 α -level across analyses of the secondary endpoints at Week 24. The secondary endpoints will be specified in a hierarchy and the first listed will be tested at the same Type I error used for the primary endpoint comparison ($\alpha = 0.05$). If this test rejects the null hypothesis, then the next listed secondary endpoint will be tested at the same Type I error rate. This testing sequence will continue as long as a null hypothesis is rejected at the 0.05 α -level. The testing sequence will be broken at the first instance that a null hypothesis is not rejected. Once the sequence is broken, no later hypothesis in the hierarchy will be tested. The order of testing for the secondary endpoints will be:

- A1C change from Baseline at Week 24
- Body weight at Week 24 change from Baseline (absolute and percent change; the absolute change will be used in the sequence of analyses)
- SBP change from Baseline at Week 16 in the subset of patients with Baseline SBP ≥ 130 mm Hg
- Percent change from Baseline in bolus insulin dose at Week 24

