Primary analysis of the primary efficacy endpoint at Week 24 will use a Cochran-Mantel-Haenszel (CMH) test stratified by BMI at Screening ($<25 \text{ kg/m}^2$, $\geq 25 \text{ kg/m}^2$), Week -2 A1C ($\leq 9\%$, $>9\%$) and use of CSII at Screening (Yes, No). Missing observations will be imputed as non-responders. A point estimate of treatment effect will be based on the sotagliflozin minus difference in binomial proportions. A 2-sided 95% CI will be estimated on the observed difference and will be based on normal approximation methods using a continuity correction factor. The individual components of the endpoint will be summarized separately using descriptive statistics.

Sensitivity analysis of the primary endpoint will use a single imputation method to obtain a rectangular dataset. Imputations will be based on use of the last observation carried forward (LOCF) algorithm. The stratified CMH test will be applied to this imputed dataset. The stratified CMH test will also be applied to the PP dataset as an additional sensitivity analysis.

Primary analysis of the continuous efficacy endpoints will use mixed-effects model for repeated measures (MMRM) statistics based on the restricted maximum likelihood (REML) method for estimation. The analysis model will include fixed, categorical effects of treatment, BMI at Screening ($<25 \text{ kg/m}^2$, $\geq 25 \text{ kg/m}^2$), Week -2 A1C ($\leq 9\%$, $>9\%$) and use of CSII at Screening (Yes, No), time (study week), baseline-dependent variable-by-time interaction, and a treatment-by-time interaction. An unstructured (co)variance structure will be used to model the within-patient errors. Other structures will be explored by use of Akaike's information criteria should the unstructured (co)variance structure not result in model convergence. The Kenward-Roger approximation will be used to estimate the denominator degrees of freedom. The adjusted mean change from Baseline by each study week for each treatment group will be estimated in the framework of this model, as well as the between-group differences (comparing sotagliflozin to placebo) and the 95% CIs for the adjusted mean. All post-Baseline observations collected at scheduled visits will be used in the MMRM, including

data collected after the discontinuation of study drug. An analysis of covariance (ANCOVA) will be applied where only 1 post-Baseline scheduled visit occurs; ie, the MMRM analysis omitting the time-related effects.

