Primary analysis of the continuous efficacy endpoints will use mixed-effects model for repeated measures (MMRM) statistics based on the restricted maximum likelihood (REML) method for estimation. The analysis model will include fixed, categorical effects of treatment, BMI at Screening ($<25 \text{ kg/m}^2$, $\geq 25 \text{ kg/m}^2$), Week -2 A1C ($\leq 9\%$, $>9\%$), use of CSII at Screening (Yes, No), time (study week), Baseline-dependent variable-by-time interaction, and a treatment-by-time interaction. An unstructured (co)variance structure will be used to model the within-patient errors. Other structures will be explored by use of Akaike's information criteria should the unstructured (co)variance structure not result in model convergence. The Kenward-Roger approximation will be used to estimate the denominator degrees of freedom. The adjusted mean change from Baseline by each study week for each treatment group will be estimated in the framework of this model, as well as the between-group differences (comparing sotagliflozin to placebo) and the 95% CIs for the adjusted mean. All post-Baseline observations collected at scheduled visits will be used in the MMRM, including data collected after the discontinuation of study drug. An analysis of covariance (ANCOVA) will be applied where only 1 post-Baseline scheduled visit occurs; ie, the MMRM analysis omitting the time-related effects.

For binary endpoints estimated as binomial proportions, the frequency and proportion of patients achieving the outcome will be presented by treatment group at each assessed study week. The primary analysis of these endpoints will use a CMH test stratified by the different levels of the randomization stratification factors of BMI at Screening ($<25 \text{ kg/m}^2$, $\geq 25 \text{ kg/m}^2$), Week -2 A1C ($\leq 9\%$, $>9\%$), and use of CSII at Screening (Yes, No). These treatment group comparisons will be performed at Week 24 only. The earlier study weeks will use descriptive analyses to summarize the data. These descriptive statistics will include the patient counts and proportions, point estimates of treatment effect, and 95% CIs of the treatment effect. Missing observations at Week 24 will be imputed as non-responders; only the observed data will be summarized at the earlier study visits. Endpoints comprised of multiple outcomes will use descriptive methods to summarize each component by treatment group at each study week.

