The test for superiority of sotagliflozin versus placebo based on the primary efficacy endpoint will be performed at the 2-sided 0.05 α -level. If this null hypothesis is rejected, a sequential procedure will be used to maintain the overall Type I error rate at a 2-sided, 0.05 α -level across analyses of the secondary endpoints at Week 24. The secondary endpoints will be specified in a hierarchy and the first listed will be tested at the same Type I error used for the primary endpoint comparison ($\alpha = 0.05$). If this test rejects the null hypothesis, then the next listed secondary endpoint will be tested at the same Type I error rate. This testing sequence will continue as long as the null hypothesis is rejected at the 0.05- α -level. The testing sequence will be broken at the first instance that a null hypothesis is not rejected. Once the sequence is broken, no later hypothesis in the hierarchy will be tested. The order of testing will be:

- A1C change from Baseline at Week 24
- Body weight at Week 24 change from Baseline (absolute and percent change; the absolute change will be used in the sequence of analyses)
- SBP change from Baseline at Week 16 in the subset of patients with Baseline SBP ≥ 130 mm Hg
- Percent change from Baseline in bolus insulin dose at Week 24

In addition, raw P-values and 95% CIs will be computed for tests of all secondary endpoint hypotheses. These raw or unadjusted statistics will be used as descriptive summaries of the data and will not be used for formal testing of the hypotheses.

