6 STATISTICAL METHODS

6.1 General Principles

All data processing, summarization, and analyses will be performed using the Hosted SAS Environment / Version 9.3 (or later) of the SAS® (SAS Institute, Cary, NC) statistical software package.

Unless specified otherwise, data will be displayed using the following treatment group labels, in the order presented:

- Placebo
- LX4211 400 mg
- Total (if applicable)

Sotagliflozin will be referred to as “LX4211” in all data displays. LX4211 is also the term used in the remaining sections of this SAP.

All data collected will be presented in listings by treatment group, center, patient, and visit (where applicable), unless otherwise specified.

Data will be presented in summary tables by treatment group, assessment, and visit (where applicable). The category “Missing” will be presented if the number missing is greater than zero for at least 1 treatment group.

Descriptive summary statistics for continuous variables will include the number of observations (N), mean, standard deviation (SD), median, minimum, and maximum.

Descriptive summary statistics for categorical variables will include frequency counts and percentages [n (%)]. Unless stated otherwise in the table shells, the denominator for percentage calculations will be the number of patients in the pertinent analysis population.

Dates will be displayed as DDMMMYYYY.

For continuous efficacy variables that are derived as percentage change from Baseline outcomes, the applied analyses and their results will be used for descriptive purposes. Exceptions to this statement are the secondary efficacy endpoints of percent change from Baseline at Week 24 in body weight and bolus insulin dose, and the other efficacy endpoints of percent change from Baseline by study visit in body weight, bolus insulin dose, total insulin dose, and basal (or non-bolus) insulin dose, where both descriptive and inferential summaries will be provided.

Analysis and summarization of treatment group comparisons for the primary and secondary efficacy endpoints will be reported in their original measurement units and converted values to accommodate regulatory review by Food and Drug Administration (FDA) and external authorities, where appropriate.

All significance tests will be 2-sided and use a 0.05 α -level unless specified otherwise.

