Mean daily bolus insulin dose will be defined as the average of daily bolus insulin doses as calculated above based on results of at least 3 days of data during the preceding 3-5 days (consecutive or nonconsecutive) prior to the clinic visit. Dose on Day 1 will be excluded from Baseline calculation. Mean daily bolus insulin dose and percent change from Baseline in mean daily bolus insulin dose at Week 24 will be summarized by treatment group using standard descriptive statistics. The treatment effects at Week 24 will be evaluated using MMRM statistics with percent change from Baseline as the endpoint and with no interaction covariate. Inferential statistics will be based on the percent change from Baseline in mean daily bolus insulin dose.

In addition, absolute change from Baseline in mean daily bolus insulin dose will be summarized using standard descriptive statistics and the treatment effect will be evaluated using MMRM statistics with change from Baseline as the endpoint and Baseline mean daily bolus insulin dose-by-time interaction as a covariate.

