7 CHANGES IN THE PLANNED ANALYSES OF THE PROTOCOL

- The protocol (Section 10.3.1.3) stated that the secondary endpoints (A1C, body weight, SBP, and bolus insulin dose) will be assessed at specified cut points. The specific cut points to use are provided in this SAP (see [Section 3.1.3](#)).

Statistical Analysis Plan

Version: Final 1.0

Lexicon Pharmaceuticals Protocol No. LX 4211.1-312-T1DM

Date of Issue: 17 MAR 2017

Covance Study ID: 000000145143

- Sensitivity analysis of the primary efficacy endpoint using the Last Observation Carried Forward (LOCF) algorithm to impute missing data will not be performed. The analysis of the primary efficacy endpoint will use NRI to impute missing data at Week 24 (see [Section 5.2.1](#)).
- Two sensitivity analyses of the primary efficacy endpoint using the same cut-off dates for SH and DKA events have been added (see [Section 6.8.2](#)).
- Summary statistics of mean bolus insulin dose, total daily insulin dose, and mean daily basal (or non-bolus) insulin dose as percent of the Baseline measure will be provided, as stated in [Sections 6.8.3.4](#) and [6.8.4.8](#).
- Analysis of the primary efficacy endpoint and the change from Baseline to Week 24 in A1C will be performed for the subgroups defined by age at study entry (<75 years, ≥75 years), sex, race, and Week -2 A1C (≤8.5%, >8.5%).
- Analysis of SBP change from Baseline to Week 16 will be performed for the subgroups defined by Baseline SBP <130 mm Hg, <140 mm Hg, and ≥ 140 mm Hg.
- EOSI events will be summarized by treatment groups across all patients (planned) and for the subgroups determined by use of CSII at Screening (Yes, No).
- For EOSIs of Malignancies of special interest, “thyroid” has been added to the list of malignancies in [Section 6.9.2](#).
- Amputations have been added to the EOSIs specifically listed in [Section 6.9.2](#) (note: per Section 9.5 of the protocol, AEs other than the EOSIs listed in the protocol may be determined to be of special interest).
- Additional overall summaries will be presented for EOSI for 3 time periods described in [Section 6.9.2](#).
- Incidence of BHB >0.6 mmol/L during Double-blind Treatment Period will be analyzed by logistic regression models.
- Incidence of treatment-emergent acidosis-related AEs will be analyzed.

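### The SAP removes the protocol's baseline-by-time covariate from the model for the last gated test (percent change in bolus insulin) without listing the change; the cost is a modest loss of precision

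*SAP*

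**What the plan says.** **Protocol.** Section 10.4.1 gives a single MMRM for the continuous efficacy endpoints. Its terms include "time (study week), Baseline-dependent variable-by-time interaction, and a treatment-by-time interaction", and the synopsis has the same term. Percent-change endpoints are not exempted. The protocol itself places "Percent change from Baseline in bolus insulin dose at Week 24" fourth and last in the testing sequence, so its own model covers that endpoint.

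**SAP.** Section 6.8 keeps the sequence but adds: "For the endpoint of percent change from Baseline, the analysis model will not include the interaction covariate". Section 6.8.3.4 repeats this for bolus insulin, analysing "percent change from Baseline as the endpoint and with no interaction covariate", and bases inference on percent change. For absolute change in the same dose, which is not the gated test, that section keeps "Baseline mean daily bolus insulin dose-by-time interaction as a covariate".

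SAP 6.1 treats percent-change results as descriptive in general, but: "Exceptions to this statement are the secondary efficacy endpoints of percent change from Baseline at Week 24 in body weight and bolus insulin dose". The model without the covariate therefore carries the formal test.

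SAP Section 7 has 12 bullets on changes from the protocol, for example: "Sensitivity analysis of the primary efficacy endpoint using the Last Observation Carried Forward (LOCF) algorithm to impute missing data will not be performed". One bullet cites Section 6.8.3.4, but only for added summary statistics. None mentions the dropped covariate.

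**The concern.** Neither document's model has a baseline main effect apart from the interaction. Dropping the interaction therefore removes every baseline dose term from the gated analysis. Expressing the outcome as a percentage of baseline does not make it independent of baseline: patients whose baseline reading is high by chance tend to show larger percentage falls. Leaving that relation unmodelled puts explainable variance into the error and leaves chance imbalance in baseline dose without direct adjustment.

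There is also a documentation problem. A reader who relies on Section 7 would not learn that the model for a confirmatory test differs from the protocol, or why.

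**Working it through.** **1. The plan's own figures.** Neither document gives an SD, correlation, effect size or power for bolus insulin. The nearest stated figures are the primary-endpoint sample sizes of 380 and 544 per arm. The two-proportion formula with rates centred on 0.50, two-sided 0.05 and 90% power gives 363 and 524 uncorrected; the continuity correction gives 380 and 544, as stated. These say nothing about bolus insulin. The inputs taken from the documents are 700 per arm, 1:1 allocation, two-sided 0.05, 20% dropout, and visits at Weeks 4, 8, 16 and 24.

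**2. Assumed inputs.** Lognormal dose with CV 40–80%; log-scale correlation between baseline and Week 24 of 0.60–0.95; cumulative missing data of 4/8/14/20%. Under these, the correlation (ρ) of percent change with baseline is −0.13 to −0.41.

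**3. Analytic check.** With complete data, the SE ratio without versus with a linear baseline term is 1/√(1 − ρ²).
- |ρ| = 0.2: 1/√0.96 = 1.021
- |ρ| = 0.3: 1/√0.91 = 1.048
- |ρ| = 0.4: 1/√0.84 = 1.091

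At |ρ| = 0.4, a test with 90% power when adjusted has power Φ((1.96 + 1.28) × √0.84 − 1.96) = 0.84 unadjusted. That equals 700 × 0.84 = 588 patients per arm.

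**4. Simulation of the planned model.** 1000 null trials per scenario, unstructured covariance, treatment-by-time and the three binary strata, fitted without and with baseline-by-time. Week 24 SE in percentage points (without / with):

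| CV | Correlation | Strata unrelated to dose | Strata strongly related to dose |
|---|---|---|---|
| 40% | 0.60 | 2.19 / 2.02 | 2.14 / 2.02 |
| 40% | 0.80 | 1.48 / 1.42 | 1.46 / 1.42 |
| 40% | 0.95 | 0.716 / 0.709 | 0.714 / 0.709 |
| 60% | 0.60 | 3.47 / 3.26 | 3.39 / 3.25 |
| 60% | 0.80 | 2.24 / 2.16 | 2.21 / 2.16 |
| 60% | 0.95 | 1.043 / 1.034 | 1.040 / 1.034 |
| 80% | 0.60 | 4.96 / 4.72 | 4.85 / 4.70 |
| 80% | 0.80 | 3.01 / 2.92 | 2.97 / 2.92 |
| 80% | 0.95 | 1.341 / 1.330 | 1.337 / 1.330 |

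With unrelated strata, the SE without the term is 0.8–4.1% larger at correlations 0.80–0.95 and 5.0–8.4% larger at 0.60. If the strata explain 20–25% of baseline dose variance, the range is 0.5–5.8%. Null rejection was 0.043–0.063 without the term and 0.042–0.060 with it.

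**5. Power**, as Φ(effect/SE − 1.96). Central case (CV 60%, correlation 0.80, unrelated strata):
- 5 points: Φ(5/2.24 − 1.96) = 0.61, against Φ(5/2.16 − 1.96) = 0.64
- 10 points: 0.994 against 0.996
- 20 points: 1.00 for both

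In sample-size terms this is 700 × (2.16/2.24)² = 651 patients per arm.

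The largest gaps in any scenario all occur at correlation 0.60:
- 5 points (CV 40%): Φ(5/2.19 − 1.96) = 0.627 against Φ(5/2.02 − 1.96) = 0.697, a gap of 7.0 percentage points
- 10 points (CV 60%): Φ(10/3.47 − 1.96) = 0.822 against Φ(10/3.26 − 1.96) = 0.866, a gap of 4.4 from the rounded SEs (4.6 unrounded)
- 20 points (CV 80%): a gap of 0.8

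**6. Chance imbalance is the same cost, not a second one.** The between-arm difference in mean baseline dose has SD √(2/700) = 0.053 baseline SDs. At the central slope of 10.5 points per baseline SD, that moves the unadjusted estimate by 10.5 × 0.053 = 0.56 points. Then √(2.16² + 0.56²) = 2.23, essentially the unadjusted SE of 2.24.

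**7. The condition on validity.** Step 4 made missingness unrelated to dose. Where missingness depends on baseline dose in opposite directions by arm (±0.3 log-odds per baseline SD), null simulations put the Type I error of the unadjusted test at about 0.06 to 0.14, depending on dose assumptions and model, against about 0.05 to 0.07 with baseline in the model. At ±0.6, a Week 24-only analysis gave 0.24–0.36 against 0.05–0.08. Nothing in the documents suggests such a pattern.

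**The case against.** The best reply is that this is small and open. The rule is stated in SAP 6.8 and repeated by endpoint, so the model is prespecified and nobody could run the wrong one. Protocol 10.4 calls its text an overview and leaves detail to the SAP. Percent change already divides by baseline, and some statisticians omit the covariate for that reason. A baseline-adjusted analysis of absolute change will also be reported. The test is last in the sequence, so failing it blocks nothing else, and the central power loss is about 3 percentage points at a 5-point effect and none at 20.

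Much of this stands. The change is not hidden, no other gated test is affected, and every figure for its size rests on assumed inputs. Three parts do not stand. Removing a specified term is a change, not added detail. Dividing by baseline does not remove the dependence, as the correlations of −0.13 to −0.41 show. The adjusted absolute-change analysis lies outside the gate and does not carry the formal test.

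**Conclusion.** The concern holds. The textual mismatch is certain: the protocol includes the term, the SAP removes it from a confirmatory test, and Section 7 is silent. The consequence is modest: a Week 24 standard error 0.5% to 8.4% larger over the assumed range, about 3.6% in the central case.

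Protocol 7.6.1.4 expects the insulin-to-carbohydrate ratio to fall by about 30%, and a protocol responder endpoint uses a bolus reduction above 20%. Neither is a Week 24 between-arm difference, but if the true difference is near 20 points the loss hardly matters. It matters more if the effect is nearer 5 points and doses track weakly over time. At |ρ| of 0.5 the SE would be 15.5% larger (1/√0.75 = 1.155), no longer modest, but the assumed dose distributions do not reach that.

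The absence of expected bias or Type I inflation is conditional on missingness not depending on baseline dose differently by arm. Restoring the covariate also gives some protection if that condition fails.

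**What to change.** In SAP 6.8 and 6.8.3.4, restore the baseline mean daily bolus dose-by-time covariate in the percent-change MMRM used for the gated test. Do the same with baseline weight for percent change in body weight (SAP 6.8.3.2); it lies outside the testing sequence but is a protocol endpoint (Protocol 10.3.1.2). Adding the term for percent change in total and basal insulin (SAP 6.8.4.8) would be for consistency only, since the SAP introduced those analyses.

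If the term stays out of the bolus model, Section 7 should say so and give the reason; that repairs the record but not the precision. Make either change before unblinding. The cost is SAP wording and one model statement, since baseline bolus dose is already collected.
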